The Biostatistics Unit (BU), within The Feinstein Institute for Medical Research (FIMR), provides state-of-the-art statistical and data management support to the research investigators at Northwell Health, as well as other medical research institutions in the New York area. Its staff of ten PhD and Masters level statisticians and two senior applications programmers has extensive experience in the design, data management, and analysis of hundreds of clinical research

projects, including over 250 clinical trials. Primary expertise is in clinical trials, diagnostic testing and screening, the development of predictive models for prognosis, and development of protocols and grant applications.

Definitions:

All patients are required to meet the Bohan & Peter (1975) diagnostic criteria for definite or probable DM or PM (see Appendix B) and be positive for at least one autoantibody (ANA $\geq 1:80$ or RNP or SSA/SSB or any of the myositis specific autoantibody). Patients with the diagnosis of definite or probable PM will require the presence of at least one myositis specific auto-antibody (antisynthetase autoantibodies (anti-Jo-1, PL-7, PL-12, EJ, OJ), anti-SRP, anti-Mi-2, anti-p140 [also known as anti-MDA5], anti-p155/140 [also known as anti-TIF], anti-NXP-2 [also known as MJ]). Patients with the diagnosis of definite or probable PM in the absence of myositis specific auto-antibodies will require review of the muscle biopsy results and adjudication of the diagnosis by a committee of 3 experts that will be predetermined in advance.

Refractory Myositis: Refractory myositis is defined as chronic IIM with an inadequate response or intolerance to at least three months of corticosteroids and/or an inadequate response or intolerance to at least three months of at least one other immunosuppressive agent (azathioprine, methotrexate, mycophenolate mofetil, leflunomide, cyclophosphamide, tacrolimus, cyclosporine or IVIG).

Core Set Measures (CSM): All enrolled subjects will be required to have active disease based on the clinical core set measures, which is a standard instrument for assessing myositis disease activity. Active disease using the CSM is defined by International Myositis Assessment and Clinical Studies Group ¹¹:

1. Manual muscle testing (MMT-8) with a score $\leq 125/150$

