2. Elevation of at least one muscle enzyme (creatinine kinase [CK]; myoglobin; alanine aminotransferase [ALT]; or aspartate aminotransferase [AST]) to a minimum level of 1.3 times the upper limit of normal.
3. Physician Global Assessment ≥ 2.0 cm using a visual analogue scale (VAS) 10.0 cm in length.
4. Patient Global Assessment ≥ 2.0 cm using a visual analogue scale (VAS) 10.0 cm in length.
5. Global extra muscular disease activity score ≥ 1.0 cm using a visual analogue scale (VAS) 10.0 cm in length. This score is based on the investigator's composite assessment of disease activity of the constitutional, cutaneous, skeletal, gastrointestinal, pulmonary and cardiac scales on the Myositis Disease Activity Assessment Tool (MDAAT).
6. HAQ disability index with a minimum value of 0.25.

The patient will be required to meet an MMT 8 score of $\leq 125/150$ as a major CSM criterion and at least 2 other CSM criteria to classify as an active disease.

In addition, for patients with ≥ 7 years of IIM, muscle biopsy or muscle MRI within 4 months prior to enrollment will be required to document active myositis to avoid enrolling patients with

significant index of damage/ muscle atrophy. This is not applicable to DM patients with a cutaneous VAS score of >3 cm on a 10 cm VAS scale (MDAAT).

Response rate: The response rate will be assessed by the percentage of patients meeting the definition of improvement (DOI). DOI is based on the definition of improvement developed by the International Myositis Assessment and Clinical Studies Group utilizing 6 core set measures.

DOI: DOI is defined as $\geq 20\%$ improvement in any 3 of the CSM, with no more than 2 CSM worsening by $\geq 25\%$ (excluding MMT)¹¹.

Definition of Worsening (DOW): Determination of worsening of the disease activity will be based on the definition of worsening (DOW) criteria developed by the International Myositis Assessment and Clinical Studies Group (IMACS) utilizing 6 core set measures¹¹:

1. worsening of Manual Muscle testing by $\geq 20\%$ and or Physician Global worsening of ≥ 2 cm on a 10 cm VAS or
2. Global extra muscular organ disease activity worsening by ≥ 2 cm on a 10 cm VAS on MDDAT, or
3. 3 of 6 CSM worse by $\geq 30\%$

Disease Flare: IIM Disease Flare is recorded when the patient:

1. reaches DOW;
2. new start or dose increase of corticosteroid or immunosuppressive agent for treatment of IIM after study week 8;

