 - b. Definite or probable diagnosis of polymyositis (PM) with presence of one of myositis specific antibodies. In the absence of myositis specific auto-antibodies, the diagnosis of PM will require review of the muscle biopsy and adjudication by the predetermined committee of experts.
- 3) Presence of positive autoantibody (ANA $\geq 1:80$ or RNP or SSA/SSB or any of the myositis specific autoantibody anti-synthetase autoantibodies (anti-Jo-1, PL-7, PL-12, EJ, OJ), anti-SRP, anti-Mi-2, anti-p140 [also known as anti-MDA5], anti-p155/140 [also known as anti-TIF], anti-NXP-2 [also known as MJ]).
- 4) Have refractory IIM as defined by inadequate response or intolerance to at least 3 months of glucocorticoids and/or an inadequate response or intolerance to at least 3 months at least one other immunosuppressive agent, such as azathioprine, methotrexate, IVIG, mycophenolate mofetil, leflunomide, tacrolimus, cyclosporine cyclophosphamide, and Rituximab.
- 5) Have active IIM at screening. This requires at least 3 criteria from the CSM (listed above) to be met for enrollment.
- 6) Dermatomyositis patients that do not meet the MMT criteria, must have:
 - a. a cutaneous VAS score of >3 cm on a 10 cm VAS scale (MDAAT) will be required:
 - b. elevation of at least one muscle enzyme (creatinine kinase [CK]; myoglobin; alanine aminotransferase [ALT]; or aspartate aminotransferase [AST]) to a minimum level of 1.3 times the upper limit of normal,
 - c. and 1 additional core set measure
- 7) For patients with ≥ 7 years of IIM, muscle biopsy or muscle MRI within 4 months prior to enrollment will be required to document active myositis to avoid enrolling patients with significant index of damage/ muscle atrophy. This is not applicable to DM patients with a cutaneous VAS score of >3 cm on a 10 cm VAS scale (MDAAT).
- 8) Have a stable background glucocorticoid therapy for at least 2 weeks prior to screening

(Prednisone (or equivalent) dose \leq 15 mg daily)

9) Immunosuppressive therapy (IS) at the time of enrollment is not required. However, a patient receiving IS therapy at the time of enrollment must be on a stable regimen (azathioprine, mycophenolate mofetil, tacrolimus, cyclosporine for \geq 2 months prior to screening. Patients on intravenous gamma globulin (IVIG) have to be on a stable dose and frequency regimen for \geq 3 months.

Therapeutic Agent	Treatment Duration prior to Screening \geq	Dose Increase prior to Screening \geq
Azathioprine	2 months	2 weeks

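### The eligibility passages disagree on whether dermatomyositis patients with MMT-8 above 125/150 may enter, and any who do must meet the primary DOI on 3 of 5 measures instead of 3 of 6

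*Combined protocol and SAP*

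**What the plan says.** Four places in the combined protocol and SAP bear on this point.

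- **Definitions, Core Set Measures.** The six measures are MMT-8, muscle enzyme, physician global, patient global, global extramuscular activity and HAQ. Each has an activity threshold; for MMT-8 it is 125 or less out of 150. The section then makes MMT-8 compulsory: "The patient will be required to meet an MMT 8 score of" 125/150 or less, together with at least two other CSM. It gives no exception for dermatomyositis (DM).
- **Inclusion Criteria, 5.** Active disease at screening: "This requires at least 3 criteria from the CSM (listed above) to be met for enrollment". MMT-8 is not singled out.
- **Inclusion Criteria, 6.** "Dermatomyositis patients that do not meet the MMT criteria, must have" a cutaneous VAS above 3 cm, at least one muscle enzyme at 1.3 times the upper limit of normal or more, "and 1 additional core set measure".
- **Definitions, DOI, and Endpoints, Primary Endpoint.** The primary endpoint is the proportion meeting DOI at 40 weeks. DOI is at least 20% "improvement in any 3 of the CSM, with no more than 2 CSM worsening by" 25% or more. It uses all six measures, and improvement in MMT-8 is not compulsory.

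The DOI text does not say how percent improvement in MMT-8 is calculated. It has no rule for a measure that starts at its ceiling or floor. The documents give no expected number of DM patients above 125.

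**The concern.** MMT-8 cannot exceed 150. Criterion 6 exists to admit DM patients whose MMT-8 is above 125, and 125 is the highest baseline from which a 20% relative gain fits on the scale. For these patients one of the six routes to improvement is closed before treatment starts, while the requirement of three improvements is unchanged.

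Two things are at stake. First, a site cannot tell from the text whether a DM patient above 125 is ineligible, needs two active CSM, or needs three. Second, a stricter response rule for part of the sample lowers the expected response rates and narrows the difference between arms. The trial has 15 patients per arm, and its sample size assumes no dropout, so it has little power to spare.

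**Working it through.** **1. The eligibility passages side by side.** Take three illustrative patients, each with MMT-8 above 125. Cutaneous VAS is not one of the six CSM, so it does not add to the CSM count.

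| Patient | Definitions | Criterion 5 | Criterion 6 read alone |
|---|---|---|---|
| DM, skin VAS above 3 cm, raised enzyme + 1 other CSM (2 CSM) | not eligible | not met | met |
| DM, skin VAS above 3 cm, raised enzyme + 2 other CSM (3 CSM) | not eligible | met | met |
| PM, 3 non-MMT CSM | not eligible | met | does not apply |

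No row gives one answer throughout. If criteria 5 and 6 apply jointly, a DM patient above 125 needs three non-MMT CSM. Definitions still excludes that patient.

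**2. The ceiling.** Maximum relative gain = (150 − baseline)/baseline.

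- 125: 25/125 = 20.0%, just attainable
- 126: 24/126 = 19.0% (a 20% gain would need 151.2)
- 130: 20/130 = 15.4%
- 140: 10/140 = 7.1%

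If 20% meant 20% of the full scale (30 points), the limit would be 150 − 30 = 120, and the conclusion would be the same. Only a definition based on the deficit (150 minus score) would make the gain attainable, and the plan states no such definition.

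**3. What this does to the DOI.** Six measures, each improved or not, give 64 patterns, of which 42 have three or more improved. In 10 of the 42, MMT-8 is the necessary third measure: C(5,2) = 10. The other 32 qualify without it. So the DOI remains reachable above 125. A patient is affected only if exactly two other measures improve and a real gain in strength is held below 20% by the ceiling.

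**4. The plan's own sample size.** Inputs from Sample Size Considerations: 5% vs 50%, two-sided alpha 0.05, 80% power, chi-square, no dropout. With pooled variance and no continuity correction:

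- n = [1.96 × √(2 × 0.275 × 0.725) + 0.842 × √(0.05 × 0.95 + 0.50 × 0.50)]² / 0.45² = (1.238 + 0.459)² / 0.2025 = 14.2, rounded up to 15. This matches the plan.
- Power at 15 per arm = Φ[(0.45 × √15 − 1.238)/0.545] = Φ(0.926) = 82.3%.

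**5. Size of the effect (illustration).** Assume that the six CSM improve independently with equal probability p, and set p so that P(at least 3 of 6) equals the planned rate. This gives p = 0.4214 for belimumab and 0.1532 for placebo. With MMT-8 unavailable:

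- P(at least 3 of 5) = 10p³(1−p)² + 5p⁴(1−p) + p⁵
- belimumab: 0.2505 + 0.0912 + 0.0133 = 35.5%
- placebo: 0.0258 + 0.0023 + 0.0001 = 2.8%

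Let f be the share of each arm admitted above 125 (assumed). The arm rate is (1 − f) × planned rate + f × reduced rate.

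| f | Belimumab | Placebo | Difference | Power, 15 per arm |
|---|---|---|---|---|
| 0% | 50.0% | 5.0% | 45.0% | 82.3% |
| 20% | 47.1% | 4.6% | 42.5% | 78.9% |
| 40% | 44.2% | 4.1% | 40.1% | 75.3% |

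For f = 40%: 0.6 × 0.50 + 0.4 × 0.355 = 0.442 and 0.6 × 0.05 + 0.4 × 0.028 = 0.041. Power = Φ[(0.4007 × √15 − 1.187)/0.535] = Φ(0.683) = 75.3%.

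**6. Sensitivity.** Exact power shows a similar drop. From f = 0 to f = 20% it goes from 87.0% to 84.2% for the uncorrected chi-square test and from 73.6% to 69.9% for Fisher's exact test. Independence is the least favourable correlation examined: at an assumed correlation of 0.3 or 0.6 between CSM, belimumab response on five measures is 40.6% or 44.0% instead of 35.5%.

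**The case against.** The strongest reply is that the DOI is any three of six and never requires MMT-8. That is correct. It rules out an inference a reader might draw, that DM patients above 125 cannot respond or that true responders are shown to be counted as failures. Such misclassification is possible, but the documents do not let anyone count it.

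A second reply is that subjects must meet the inclusion criteria together, so criterion 5 already obliges a DM patient above 125 to have three active non-MMT CSM. That is a fair reading. It weakens any claim that patients with only two active measures are clearly let in. It does not resolve the conflict with Definitions, which requires MMT-8 of every patient.

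Third, one might suppose that only the measures active at entry can improve, which would make the loss far larger. The plan does not say so. The thresholds define active disease for enrolment, and the DOI has no condition that a measure be above its threshold at baseline. A physician global of 1.8 cm can still fall by 20%.

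Fourth, skin benefit is not outside the primary endpoint. Cutaneous VAS is not itself a CSM, but the global extramuscular score is based on a composite that includes the cutaneous scale.

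Finally, nothing says that the planned 50% excludes patients admitted under criterion 6. Treating it as the rate for patients with six movable measures is a modelling choice. This objection stands, so the power figures are an illustration and not an estimate for this trial.

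**Conclusion.** Two findings hold from the documents alone. Definitions, criterion 5 and criterion 6 contradict each other on eligibility above MMT-8 125. Any DM patient admitted above 125 has no route to a 20% relative gain in MMT-8, so must reach the DOI on three of the other five measures.

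The statistical cost is moderate. Under the stated assumptions it is about 3.4 points of power if 20% of patients enter this way (82.3 − 78.9) and 7.0 points if 40% do (82.3 − 75.3). It rests on independent, equally likely CSM, on calibration to 50% and 5% with six movable measures, and on assumed shares.

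A reader might infer a bias towards one arm. The documents do not support that: the ceiling applies in both arms, allocation is 1:1 and disease type is a stratification factor. What is expected is lower response in both arms and a smaller difference. Chance imbalance remains possible, because MMT-8 is not a stratification factor and the primary test is unadjusted. Nor is the planned 15 per arm a miscalculation; it reproduces from its own inputs.

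**What to change.** 1. **Reconcile Definitions (Core Set Measures) with inclusion criteria 5 and 6.** One rule should state whether DM patients above 125 are eligible and how many non-MMT CSM they need, bearing in mind that the DOI requires three improvements. It should also say whether criterion 5 dispenses with the MMT-8 condition for anyone else. Which rule to adopt is for the sponsor to decide.
2. **Add a supportive analysis to Statistical Methods.** Pre-specify week-40 DOI by arm in patients with baseline MMT-8 of 125 or less, and report the number above 125 by arm. The subset is defined before randomisation, so the comparison within it remains a randomised one. Name the baseline visit, since MMT-8 is recorded at both Screening and Day 0.
3. **Add one sentence to the DOI definition** on how percent improvement in MMT-8 is calculated and how a measure at its ceiling or floor at baseline is counted.

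The cost is a short amendment and a few lines of analysis text, with no new data. The supportive subset would be small: 24 of 30 patients if 20% are above 125 (0.8 × 30), or 18 if 40% are (0.6 × 30). Depending on how the passages are reconciled, a few DM patients with mainly skin disease may become ineligible.

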3. Have a history of a primary immunodeficiency
4. Have a significant IgG deficiency (IgG level < 400 mg/dl) Have an IgA deficiency (IgA level < 10 mg/dL)
5. Discontinuation IS agent < 3 months prior to Screening. Including: azathioprine, methotrexate, mycophenolate mofetil, leflunomide, tacrolimus, cyclosporine, or intravenous gamma globulin [IVIG]
6. Have received Rituximab within 365 days prior to Screening.
7. Have received cyclophosphamide within 180 days prior to Screening
8. Have received treatment with:
 - a. Initiated IVIG less than 3 months prior to Screening
 - b. Pulse steroids 2 months prior to Screening
9. Have received treatment with Belimumab at any time prior to Screening
10. Have received a biologic investigational agent within 365 days prior to Screening.
11. Have received a non-biologic investigational agent within 30 days or 5 half-lives of the agent (whichever is longer) prior to Screening.
12. Have a history of an anaphylactic reaction to parenteral administration of contrast agents, human or murine proteins or monoclonal antibodies.
13. Infection history:
 - a. Currently on any suppressive therapy for a chronic infection (such as tuberculosis – including latent tuberculosis, pneumocystis, cytomegalovirus, herpes simplex virus, herpes zoster and atypical mycobacteria).

NOTE: Testing for latent TB is a standard of care for patients on immunosuppressive therapy and results will be obtained from their medical record. If no TB history is found for these patients, a Quantiferon Gold or PPD test will be performed prior to Day 0 as part of standard of care.

 - b. Hospitalization for treatment of infection within 60 days of Day 0.
 - c. Use of parenteral (IV or IM) antibiotics (antibacterials, antivirals, anti-fungals, or anti-parasitic agents) within 60 days of Day 0.
14. Have a historically positive HIV test or test positive at screening for HIV.
15. Have a history of autoimmune hepatitis
16. Hepatitis status will be obtained from patients' medical records. If unavailable, testing will be done as part of standard of care. Patients are excluded if there is evidence of chronic or active Hepatitis B infection with:
 - a. Hepatitis B:

- i. Presence of positive Hep B surface antigen independent of history of previous exposure to IVIG.
- ii. Positive hepatitis B core antibody for patients with no exposure to IVIG

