- iii. Patients who previously received IVIG and have positive core antibody (Hepatitis B coreAb) and negative Hep B surface antibodies with or without the presence of positive HBVDNA by PCR
- Note: Patients who previously received IVIG and with Hep B core IgG pos and Hep B sAB pos. are allowed to be enrolled but additional safety monitoring procedures must be followed on these patients – please see Appendix C: Follow Up Assessments. The table below describes which types of patients would be eligible based on different Hep B core/surface ab positivity.

Hep Bs ag	+	-/+	-/+	-	-	-
Hep B s ab	-/+	+	-/+	-	-	+
Hep B core ab IgM	-/+	+	-/+	-	-	-
Hep B core ab IgG	-/+	-/+	-/+	+	+	+
					repeat	
Hep B by PCR	-/+	-/+	+	-	-	-
STATUS:	Not eligible	Not eligible	Not eligible	Not eligible	Eligible	Eligible

- b. Hepatitis C:
 - c. Positive hepatitis C antibody with confirmatory hepatitis C viral load by PCR.
- 17. Clinically significant elevation of GGT ($>1.5 \times \text{ULN}$), bilirubin ($>1.25 \times \text{ULN}$, direct 35%), or INR (>1.2 , excluding patients on anti-coagulant therapies) or other clinically significant abnormal laboratory value in the opinion of the investigator.
- 18. Have current drug or alcohol abuse or dependence, or a history of drug or alcohol abuse or dependence within 364 days prior to Day 0.
- 19. Have evidence of serious suicide risk including any history of suicidal behaviour in the last 6 months and/or any suicidal ideation in the last 2 months or who in the investigator's judgment, pose a significant suicide risk.
- 20. Have any concurrent significant medical or psychiatric illness that the investigator considers would make the candidate unsuitable for the study.

Study Drug Administration:

1. **The study agent will be administered by 10mg/kg dose** at 2 weeks intervals for the first 3 doses and every 4 weeks thereafter. It is administered IV over a minimum of 1 hour. During the study visit at each dosing the patient will be monitored and routine laboratory testing will be performed according to standard of care. See Appendix A for infusion dosing schedule.

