- Post study follow up phone call with subject conducted at Week 72 and 84.
- Patients who previously received IVIG and with Hep B core IgG positive and Hep B sAB positive will undergo surveillance with Liver function test, Hepatitis Panel and Viral Load every 3 months.

Data Safety Monitoring Plan:

The principal investigator and two independent physicians, designated by the Principal Investigator, will be responsible for the oversight of the data safety monitoring plan. The committee will meet every 6 months to evaluate the rate of unanticipated adverse events. If any

safety signals are identified, recommendations to changes in the protocol or consent will be defined by the committee. Benefit-to-risk assessment will be made in order to determine if the study should continue. The results of these regular meetings will be recorded and disseminated to all participating clinical sites.

Feinstein Biostatistics Unit BUDDY System: Data Management

The Biostatistics Unit (BU), within The Feinstein Institute for Medical Research (FIMR), provides state-of-the-art statistical and data management support to the research investigators at Northwell Health as well as other medical research institutions in the New York area. Its staff of ten PhD and Masters level statisticians and two senior applications programmers has extensive experience in the design, data management, and analysis of hundreds of clinical research projects, including over 250 clinical trials. Primary expertise is in clinical trials, diagnostic testing and screening, the development of predictive models for prognosis, and development of protocols and grant applications.

The Biostatistics Unit provides data management support through its “BUDDY” system (“Biostatistics Unit Database Designed for You”). BUDDY is a highly customized, secure, HIPAA-compliant, web-based database application. It is particularly suited to studies with longitudinal and relational data structures, especially clinical trials. The cost of database development may vary depending upon features requested by the user, including, but not limited to: case report form development, number of unique data screens, transfer of data between another system and BUDDY, data validation checks between screens, image file storage, special queries or reports, translation of adverse event descriptions into MedDRA, and data submission tracking.

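### Exclusion 16a, its Note and the hepatitis B table do not give one eligibility rule for core-antibody-positive patients

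*Combined protocol and SAP*

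**What the plan says.** Item 16 of the Exclusion Criteria opens: "Patients are excluded if there is evidence of chronic or active Hepatitis B infection with" the findings then listed. For hepatitis B these are:

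- 16a(i): "Presence of positive Hep B surface antigen independent of history of previous exposure to IVIG".
- 16a(ii): "Positive hepatitis B core antibody for patients with no exposure to IVIG".
- 16a(iii): "Patients who previously received IVIG and have positive core antibody (Hepatitis B coreAb) and negative Hep B surface antibodies". The item goes on to make the DNA result immaterial: "negative Hep B surface antibodies with or without the presence of positive HBVDNA by PCR".

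The Note then gives a permission, subject to extra monitoring: "Patients who previously received IVIG and with Hep B core IgG pos and Hep B sAB pos. are allowed to be enrolled". It introduces the table with "The table below describes which types of patients would be eligible based on different Hep B core/surface ab positivity". As printed, the table reads:

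| Column | Surface antigen | Surface antibody | Core IgM | Core IgG | PCR | Status |
|---|---|---|---|---|---|---|
| 1 | + | -/+ | -/+ | -/+ | -/+ | Not eligible |
| 2 | -/+ | + | + | -/+ | -/+ | Not eligible |
| 3 | -/+ | -/+ | -/+ | -/+ | + | Not eligible |
| 4 | - | - | - | + | - | Not eligible |
| 5 | - | - | - | + (*repeat* printed beneath) | - | Eligible |
| 6 | - | + | - | + | - | Eligible |

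There is no row for IVIG exposure.

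Periodic surveillance is set in Study Procedures & Assessments: "Patients who previously received IVIG and with Hep B core IgG positive and Hep B sAB positive will undergo surveillance". Appendix C, under its follow-up assessments, names the same population. Separately, the increased-monitoring criteria in Appendix C require an HBV DNA test in any subject with past IVIG whose ALT or AST rises above 2.5 times the upper limit of normal.

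**The concern.** This is a safety exclusion, and a site has three sources to apply: the numbered items, the Note and the table. If they disagree, the same serology can be enrolled at one site and refused at another, and both can point to the protocol. The patterns are foreseeable here, because IVIG is both a qualifying prior treatment and a permitted background treatment.

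Exposure is long. Under Study Design, the belimumab arm is infused from week 0 to week 64, and the placebo arm receives belimumab from week 40 to week 64, with several immunosuppressants allowed alongside. The surveillance rule is written for one serology group only, so a patient admitted by a different route may not be in it.

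**Working it through.** No sample size or power figure is involved. The check compares two logical rules over every possible result.

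**Inputs.** There are six yes/no items: past IVIG, surface antigen, surface antibody, core IgM, core IgG and PCR. That gives 2^6 = 64 patterns. Core antibody positive is taken to mean IgM or IgG positive, which is an assumption, since 16a(ii) and (iii) do not name the class. The text status comes from 16a(i)-(iii) plus the Note, and the table status from the six columns as printed.

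**Excluded by the text but matching an Eligible column: 3 patterns.** All are surface antigen negative, IgM negative, IgG positive and PCR negative.

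| Pattern | IVIG | Surface antibody | Text | Table |
|---|---|---|---|---|
| (a) | yes | - | excluded by 16a(iii) | columns 4 and 5, opposite status |
| (b) | no | - | excluded by 16a(ii) | columns 4 and 5, opposite status |
| (c) | no | + | excluded by 16a(ii) | column 6, Eligible |

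**Admitted by the Note but Not eligible in the table.** The Note's group with surface antigen negative has 2 (IgM) x 2 (PCR) = 4 patterns:

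- IgM -, PCR -: column 6, Eligible. Text and table agree.
- IgM -, PCR +: column 3, Not eligible.
- IgM +, PCR +: columns 2 and 3, Not eligible.
- IgM +, PCR -: column 2, Not eligible.

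So 3 of these 4 conflict, and in each the table is the stricter source. A further 6 patterns are barred only by the table, but the Note does not expressly admit them.

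**What *repeat* could mean.** The word stands on a line between core IgG and PCR. If it is a repeat PCR, 16a(iii) still excludes an IVIG-exposed patient, because DNA status is immaterial there. The same holds if it is a repeat core IgG that stays positive. If it is a repeat core IgG that turns negative, the conflict weakens, but no text says that the repeat decides, and the printed value is positive.

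**Surveillance.** Patterns (a), (b) and (c) all fall outside the periodic rule, which needs IVIG exposure, core IgG positive and surface antibody positive together. Pattern (a) keeps the ALT/AST-triggered HBV DNA test. Patterns (b) and (c) have neither; for them Appendix C provides hepatitis serology only after a liver stopping event.

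**The case against.** The best reply has four parts.

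1. *Column 5 may be damaged.* Two columns with identical printed results, opposite status and a stray word suggest that cell content was lost when the table was read from PDF. This stands as a caveat: column 5 must be checked against the original layout. It does not explain the word, which is defined nowhere.

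2. *16a(ii) governs whatever the table shows.* Meeting any one exclusion is enough, and the table sits inside a Note about IVIG patients. This stands, so the missing IVIG row is a scope gap and not a flat contradiction. It remains worth closing: the introducing sentence does not limit the table to IVIG patients, and column 1 restates 16a(i), which applies regardless of IVIG history.

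3. *The Note and the table can be read together*, the Note naming the group and the table adding the DNA and IgM conditions. That is a reasonable reading, and the lead-in on chronic or active infection may also bear on DNA-positive patients. But the Note states a permission and attaches only monitoring to it.

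4. *A safeguard remains.* The ALT/AST-triggered DNA test covers all past-IVIG subjects. This stands for pattern (a) only.

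A reader might also infer that the table lets DNA-positive patients in, against the text and outside surveillance. The documents do not support this. No PCR-positive pattern is Eligible in the table. A DNA-positive patient enrolled under the Note would be enrolled against the table and would be inside the surveillance population.

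**Conclusion.** The inconsistency is real, in three parts of unequal strength. As printed, column 5 conflicts with 16a(iii) and with column 4, subject to what *repeat* means and whether a value was lost. The Note lacks the PCR and IgM conditions that columns 3 and 2 impose; this does not depend on column 5. The table's silence on IVIG is a scope gap, because 16a(ii) still applies.

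The size is 3 patterns excluded by the text but matching an Eligible column, and 3 admitted by the Note but Not eligible in the table, out of 64. These count logical patterns, not patients. The documents give no serology frequencies, so the number affected among the 30 planned patients cannot be computed.

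The consequence for monitoring is limited to patients admitted through column 5, or through column 6 without IVIG exposure. They would be outside periodic surveillance, although the IVIG-exposed among them keep the triggered test. It would be too strong to say that three of the six columns admit patients wrongly: column 3 is stricter than the Note, and column 6 agrees with the Note for the IVIG-exposed patients it concerns.

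**What to change.** Reconcile 16a(i)-(iii), the Note and the table into one rule. Specifically:

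- State whether the table applies only to IVIG-exposed patients or to everyone, and show IVIG status accordingly.
- Check column 5 against the source layout, then say what *repeat* refers to and which result decides.
- Make the DNA and IgM conditions agree between the Note and the table.
- Check that the populations in Study Procedures & Assessments and in both Appendix C rules match the patients the reconciled rule admits. The two periodic rules also differ on interval (every 3 months against every 2 months); that separate discrepancy can be reconciled in the same edit.

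Which serology patterns are eligible, and how they are monitored, is for the sponsor to decide. The cost is protocol wording in an amendment; the sample size and analysis are unaffected.
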